## 1. Objectives

- 1.1. The objective of this research is to perform a non-masked, non-inferiority randomized controlled trial to assess the quality of life (QOL) of women with idiopathic overactive bladder (OAB) before and after treatment with percutaneous tibial nerve stimulation (PTNS) or transcutaneous electrical nerve stimulation (TENS) of tibial nerve. The target population is patients with OAB who previously failed first- and second-line treatments and desire non-surgical management.
- 1.2. Our central hypothesis is that a TENS unit is non-inferior to PTNS for improving the quality of life and symptom distress of women with OAB. The specific aims are:
  - 1.2.1. To compare the effects on health-related quality of life (HRQoL) and symptom bother as measured by the change in score from baseline of the Overactive Bladder questionnaire (OAB-q) in women with urgency urinary incontinence or overactive bladder before and after PTNS versus TENS after 3 months of therapy. Secondary outcomes related to this aim include change in symptom bother alone, as measured by the OAB-q symptom subscale and change in HRQL alone, as measured by the OAB-q HRQL subscale from baseline. **Hypothesis:** TENS will demonstrate similar effects on symptoms and symptom-associated HRQoL in the treatment of women with OAB compared to PTNS.
  - 1.2.2. To compare the rates of treatment success, as defined as 50% or more reduction of urinary incontinence episodes or 25% or more reduction in day or night voids in women with OAB before and after PTNS versus TENS after 3 months of therapy. The number of urinary incontinence episodes, number of voids per day and number of voids per night will be measured by a three-day voiding diary. **Hypothesis:** TENS will demonstrate similar rates of treatment success in women with OAB compared to PTNS.
  - 1.2.3. To perform a comparative analysis of patient satisfaction and compliance between TENS and PTNS. Patient satisfaction will be measured by a patient satisfaction question (PSQ). Patient compliance will be measured by number of treatment sessions completed as verified by clinical records of completed PTNS treatments and TENS device interrogation. **Hypothesis:** Women will be satisfied with both TENS and PTNS treatment and will have greater treatment compliance with TENS compared to PTNS.

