4.2.2. Exclusion Criteria

- Age  $< 18$  years
- Presence of urinary fistula
- Male genital anatomy
- Undergoing evaluation or treatment of recurrent (2 or more infections in the last 6 months or 3 or more infections in the last 12 months) or current urinary tract infection
- Current Bladder stones
- Bladder cancer or suspected bladder cancer
- Gross Hematuria
- Pregnancy or planning to become pregnant during the study
- Cognitive impairment
- Central or peripheral neurologic disorders such as multiple sclerosis, Parkinson's disease, spina bifida, spinal cord lesions, etc.
- Metal implants such as pacemaker, implantable defibrillator, or metal implants where PTNS or TENS device needs to be placed (ankle/leg)
- Uncontrolled diabetes
- Diabetes with peripheral nerve involvement

PROTOCOL TITLE: INTENSE: INvestigation of TENS Efficacy versus Posterior Tibial Nerve Stimulation for overactive bladder

- Current use of anticoagulants (excluding aspirin)
- Current use of anticholinergics or use within the last 4 weeks
- Current use of botox bladder injections or bladder botox injection within the last year (12 months)
- Current use of sacral neuromodulation therapy or currently implanted sacral neuromodulation device or leads
- Bladder outlet obstruction
- Urinary retention or gastric retention
- Painful Bladder Syndrome/Interstitial Cystitis
- Unable to be contacted for follow up by telephone
- Inability to speak/read/understand English or Spanish

4.3. We have decided to only include adults (age  $\geq 18$  years) who are capable of giving informed consent. Children, pregnant women and prisoners will be excluded.

4.4. We will include English and Spanish speaking populations only, as our primary outcome measures have not been validated in other languages. We are excluding men as we are a Urogynecology practice and therefore do not treat that population.

4.4.1. Because we are excluding pregnant women, during participant recruitment women will be asked if they are pregnant or have plans to become pregnant in the next 3 months. Their sexual activity, menopause status and surgical history (specifically hysterectomy or tubal ligation) will also be determined, which are standard questions asked in our practice for new patients. If there is concern for pregnancy, we will perform a urine pregnancy test of the participant on the day of enrollment.

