## 5. Number of Subjects

5.1. This is a single-center study at the University of New Mexico, therefore the total number of subjects at the University of New Mexico is the total number of subjects for the study.

5.2. The total number of subjects to be recruited at this site is up to 130 patients.

5.3. *Sample size calculation:* The primary outcome for this study is the change in the OAB-q total score from baseline to 3 months. We used the means and standard deviation for this questionnaire from an unpublished pilot RCT study from Walter Reed that compares PTNS and TENS for the treatment of OAB (unpublished work). We have powered the study based on a 10-point difference as significant between groups. This 10-point difference used for the power calculation is based on the previously established minimum important difference. To achieve power for this non-inferiority RCT study showing that the difference between groups is less than 10 points, we need 40 patients per group (80 total) to detect no difference with  $\alpha = 0.05$  and 80% power. Allowing for dropout of up to 30%, we will aim to randomize 114 patients, and will plan to recruit up to 130 to allow for potentially higher drop-out, as the study primary outcome is at the 12 weeks' time point. As we plan to perform both per-protocol and intention-to-treat analysis, the sample size must be met for both per-protocol and intention-to-treat analysis, with the per-protocol patients (those in the PTNS group completing at 12 treatments in a total of 13 weeks) being expected to be a lower sample size.

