### 13.Data Analysis

- 13.1. *Data Analysis:* Between and within group differences will be evaluated using Fisher's exact test for categorical variables and t-tests for continuous variables, as we expect the data will be normally distributed. Wilcoxon rank-sum test will be used for continuous variables that are not normally distributed. If there are any baseline differences between groups, a multivariate analysis will determine the contribution of these differences to observed differences (if any) between groups.
- 13.2. *Intention-to-treat analysis:* We plan to perform the primary analysis as "intention-to-treat" indicating that patients will be analyzed in the group to which they were randomized, regardless of compliance with study procedures, unless they asked to be withdrawn or were withdrawn by investigators due to safety or validity concerns. For example, PTNS patients that miss more than one session or do not make up a missed session of their office PTNS would still be analyzed in the "intention-to-treat" analysis as being in the PTNS group.
- 13.3. *Per protocol analysis:* We plan to perform a secondary analysis as "per protocol" indicating that patients will be analyzed in the group to which they were randomized only if they complete a full 12 weeks of treatment in compliance with study procedures, meaning that women assigned to the PTNS arm completed 12 weekly PTNS sessions in the office in 13 weeks or less, and women in the at-home TENS arm performed TENS stimulation at least 5 days per week for 12 weeks, as averaged over 12 weeks. For example, PTNS patients that miss more than one session or do not make up a missed session of their office PTNS will not be analyzed in the "per protocol" analysis as being in the PTNS group.
- 13.4. *Power Analysis:* Power analysis was performed based on previously reported means and standard deviation for the OAB-q. The primary outcome of this study is improvement in HRQL and symptom bother of OAB/UUI as measured by the OAB-q. We used the means and standard deviation for this questionnaire from a prior unpublished pilot RCT from Walter Reed comparing PTNS and TENS for the treatment of OAB. We have assumed a change score of greater than 10 points to be significant between groups based on the minimally important difference that has been previously established. To achieve significance for a non-inferiority study using these assumptions we would need 80 patients,

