#### **15. Withdrawal of Subjects**

Participants may withdraw from the study at any time without penalty and will continue to receive the clinical standard of care. A subject may be withdrawn from the study without her consent at the discretion of the physician and study staff if they believe she no longer meets study inclusion criteria or if she meets exclusion criteria, if they believe that it is not in her best interest to continue study participation i.e., desire to undergo alternative treatment, or if they stop the study early due to scientific reasons. Investigators may withdraw a subject if the subject is not following the study protocol. If a woman is withdrawn from the study either at her own discretion or that of the research staff, she may continue with conservative or surgical management of her OAB/UUI in the usual fashion. If a participant chooses to withdraw from the study, the study intervention and PTNS device will no longer be provided to the participant and may not be available for purchase. If a participant withdraws from the TENS group, the TENS device they purchased will be kept by the participant.

To minimize withdrawal from the study, patients will be randomized after they have had what they feel to have been adequate time to consider whether or not they would like to participate in the study and they provide consent. According to the 2010 CONSORT guidelines, we will analyze all participants assessed for eligibility within the study. We will document reasons for withdrawal from the study if the participant willingly provides this

PROTOCOL TITLE: INTENSE: INvestigation of TENS Efficacy versus Posterior Tibial Nerve Stimulation for overactive bladder

information. We will report eligibility criteria not met or reasons for declining participation in the study if the participant willingly provides this information. The withdrawal procedure is clearly documented in the study consent.

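### Women who leave before the 3-month diary get no treatment-success score, so the rate is computed among stayers and the between-arm comparison can be biased in either direction

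*Combined protocol and SAP*

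**What the plan says.** **Endpoint.** Section 1.2.2 defines success as "50% or more reduction of urinary incontinence episodes or 25% or more reduction in day or night voids", taken from a three-day diary before treatment and after 3 months. The hypothesis is that "TENS will demonstrate similar rates of treatment success in women with OAB compared to PTNS". No margin, expected rate or power is given for it. Section 7.1 lists the component counts as secondary endpoints, not the success rate itself.

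**Withdrawal.** Under section 15, staff may at their discretion withdraw a woman "if they believe that it is not in her best interest to continue study participation i.e., desire to undergo alternative treatment", or "if they believe she no longer meets study inclusion criteria or if she meets exclusion criteria". The exclusions in 4.2.2 include "Current use of anticholinergics or use within the last 4 weeks", and also bladder botox injections and sacral neuromodulation. Starting one of these other OAB treatments would therefore meet an exclusion. Section 15 records reasons for withdrawal only when the woman volunteers them.

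**Analysis.** Section 13.2 analyses women in their randomised group "unless they asked to be withdrawn or were withdrawn by investigators due to safety or validity concerns". Section 13.1 names Fisher's exact test for categorical variables. Section 13 has no missing-data method, no non-responder rule and no rule for a change of OAB treatment. Section 12.1 promises continued outcome collection for women who miss sessions, in both arms; nothing comparable is said of withdrawn women. Section 15 also cites CONSORT 2010 for analysing everyone screened for eligibility, which cannot be squared with 13.2.

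**Dropout.** Section 5.3 sets 114 as the number to randomise, "Allowing for dropout of up to 30"%.

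**The concern.** A woman who gives up her assigned treatment for another one is usually a non-responder, and a responder endpoint can classify her without further data. Under the plan as written she contributes nothing. Her arm loses a non-success from its denominator and its reported rate goes up.

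If the two arms lose different numbers of such women, the comparison in 1.2.2 is distorted. A real TENS deficit could be hidden and the similar-rates hypothesis wrongly supported, or a modest deficit could be exaggerated. A model or imputation for the OAB-q change score would not settle this, because it does not say whether a woman who switched treatment counts as a success. That has to be defined.

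**Working it through.** **1. The plan's own figure.** Section 5.3 needs 80 evaluable women: 80 / (1 − 0.30) = 114.3, against 114 stated, so it reproduces. At 1:1 that is 57 per arm, and 30% of an arm is 0.30 × 57 = 17.1, about 17 women. This figure was set for the OAB-q. The documents give no figure for treatment success that could be reproduced.

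**2. Where each route leads.**

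| Route | Under 13.2 | 3-month diary | Success score |
|---|---|---|---|
| Misses sessions, stays in study | kept | promised (12.1) | from diary |
| Asks to be withdrawn | removed | not promised | none |
| Withdrawn for safety or validity | removed | not promised | none |
| Withdrawn for best interest, without asking | not expressly removed | not promised | none |
| Withdrawn because an exclusion is met | removed only if this counts as validity | not promised | none |

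The last four rows end alike: without a diary or a scoring rule, the woman cannot enter the Fisher table.

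**3. Effect within an arm.** Let N be randomised, s the successes, and k the leavers who are not successes. The rate moves from s/N to s/(N − k), a multiplication by N/(N − k), which exceeds 1 whenever k > 0. With N = 57 and an assumed s = 28:

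- k = 0: 28/57 = 49.1%
- k = 6: 28/51 = 54.9%
- k = 12: 28/45 = 62.2%
- k = 17: 28/40 = 70.0%

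**4. Effect between arms.** Assume 34/57 = 59.6% success on PTNS and 28/57 = 49.1% on TENS, a true deficit of 6/57 = 10.5 points.

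| PTNS dropped | TENS dropped | PTNS rate | TENS rate | Apparent TENS deficit |
|---|---|---|---|---|
| 0 | 0 | 34/57 = 59.6% | 28/57 = 49.1% | 10.5 |
| 3 | 9 | 34/54 = 63.0% | 28/48 = 58.3% | 4.6 |
| 3 | 12 | 34/54 = 63.0% | 28/45 = 62.2% | 0.7 |
| 6 | 6 | 34/51 = 66.7% | 28/51 = 54.9% | 11.8 |
| 9 | 3 | 34/48 = 70.8% | 28/54 = 51.9% | 19.0 |

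(Deficits are taken from unrounded rates.) Equal losses change the gap little; unequal losses can nearly erase it or nearly double it.

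**The case against.** **A reader might infer that sections 15 and 13.2 together drop every woman who wants another treatment.** The text does not go that far. Withdrawal under section 15 is discretionary, and the staff-initiated best-interest route is not among the exceptions in 13.2. Only women who ask to leave, or whose withdrawal is put down to safety or validity, are expressly removed. Section 15's sentence on analysing everyone also points the other way. What stands is that the best-interest group still has no diary and no score, and that the two sections contradict each other.

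**A reader might infer that the bias favours TENS.** The documents do not support a direction. Women are approached when interested in PTNS (section 12), and withdrawn women are offered the usual options (4.1), so a TENS woman who is not improving has a reason to leave. But section 2 describes the weekly PTNS visits as a barrier, and 1.2.3 predicts better compliance with TENS. Heavier loss in either arm is plausible.

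**Leavers may not be failures.** A 25% reduction in day or night voids is enough for success. A woman could reach it and still leave because of visits, travel or cost. Counting switchers as not a success is a composite definition: a common choice, but a choice.

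**Scoring every loss as failure has its own bias.** Assume 60% against 45% success among stayers, and 30% uninformative loss in each arm. Then 0.70 × 60 = 42% and 0.70 × 45 = 31.5%, so a 15-point gap shrinks to 10.5, towards the similar-rates hypothesis. This stands, and it argues against using that scoring as the main method for unexplained losses.

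**The endpoint is secondary.** It has no margin or power, and 13.2 is written for the primary analysis. This also stands, and limits the weight of the point. But no other analysis set is given for treatment success.

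**Conclusion.** The concern holds. The plan removes some leavers by rule and leaves the rest without a score, so the treatment-success rate is in effect a rate among stayers. Within an arm, losing non-responders always raises the rate. Between arms, the sign and size depend on who leaves, which the documents do not tell us. In the assumed example, a 10.5-point TENS deficit could be reported as anything from 0.7 to 19.0 points under the loss patterns shown.

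Those figures rest on assumed success counts (34 and 28 of 57), assumed numbers of leavers, and the inference that the leavers are not successes. Only the 57 per arm and the overall 30% dropout allowance come from the plan, and that allowance covers dropout for any reason, not failures in one arm. This is a point to correct before the data are seen, at the weight of a secondary aim. The same exception in 13.2 also affects the primary OAB-q analysis.

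**What to change.** Make these changes to 1.2.2, 13.2 and section 15, together with the corresponding repair to 13.2 for the OAB-q:

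- Delete the 13.2 exception for this endpoint and reconcile 13.2 with section 15's sentence on who is analysed.
- State that all randomised women are in the denominator.
- Still request the 3-month diary after treatment stops or the woman leaves, where she agrees.
- Score as not a success any woman documented, before the 3-month diary, as leaving for or starting another OAB treatment, or as stopping for lack of benefit or an adverse effect.
- For women lost with no reason, use multiple imputation by arm, with not-a-success scoring as a sensitivity analysis.
- Add a record of other OAB treatment started to the existing week 6 and week 12 contacts. Table 1 has no such item, and volunteered withdrawal reasons will not be complete.

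**Cost.** One extra data item at contacts that already take place, some effort to obtain diaries from women who have stopped, and analysis wording. Stated success rates will be lower in both arms. A woman who switches because of burden or cost will count as not a success, and the report should say so. No treatment or clinical rule changes.

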## **16. Data Management/Confidentiality**

Participants will be given a de-identified study subject number. Data collection sheets and questionnaires will contain the subject number. No other patient identifiers will be collected on study forms. PHI including patient name, date of birth, phone number, email address and medical record number will be collected to track appointments and ensure patient follow-up. The data collection, HIPAA and consent forms will be maintained in a locked file cabinet in the locked Eubank research office or via REDCap. A separate folder will be designated for each participant. PHI will not be entered into the study database. The link between PHI and study IDs will be kept on a password protected computer on a secure UNM OBGYN department server.

The study database does not include sensitive information or information requiring additional protection.

Study binders will be kept in a locked cabinet in the research administrative area. In order to further ensure patient confidentiality, the identifying information will be kept separately from the numbered study files in a locked cabinet.

Electronic data entry will be performed on REDCAP, using the de-identified subject study number. The electronic data and subject link will be encrypted, password protected, and stored on the secure UNM OBGYN department server. This server's electronic security is monitored / maintained by the Health Sciences Library and Informatics Center (HSLIC). A REDCAP database will be created to collect, store and manage the data. REDCAP databases are reposed securely and all data entered is de-identified. The REDCAP database is only accessible using an individual unique login and password and access is only provided to co-investigators. Access is restricted to co-investigators and research staff and will be protected using the unique REDCAP login and password provided to each co-investigator.

Access to the files and REDCAP will be restricted to research personnel and Investigators and will be locked or password-protected using the unique REDCAP login and password provided to each co-investigator. The data will be stored for 6 years after completion of analysis and study closure and then will be destroyed.

A Certificate of Confidentiality will not be used to protect data from forced release. No identifying or study related data will be transported to outside locations. There will be no audio or video recordings or photographs taken.

## **17. Data and Specimen Banking**

As stated above, the data collection, HIPAA and consent forms will be maintained in a locked file cabinet in the Eubank research area. A separate file will be designated

PROTOCOL TITLE: INTENSE: INvestigation of TENS Efficacy versus Posterior Tibial Nerve Stimulation for overactive bladder

for each participant. A key matching study number to subject's name will be stored on a password protected computer on a secure UNM OBGYN department server. In order to further ensure patient confidentiality, the identifying information will be kept separately from the numbered study files in a locked cabinet. The data will be maintained for 6 years after completion of the study and then destroyed.

## 18. Risks to Subjects

Risks of enrollment in the study include loss of confidentiality. We will take every measure to try to ensure the security and confidentiality of participants. Participants will be recruited in a private room or in a private location via phone or HIPAA compliant ZOOM and will have ample time to consider whether they want to participate in the study. Also, locked cabinets will be used to protect patient consent information and collected data. The link identifying patients and their study numbers will be also stored on a password protected computer on a secure UNM OBGYN department server.

Additionally, each patient who will be offered enrollment will already have agreed to non-surgical management of her OAB. There are minimal risks with being assigned to either study intervention in this RCT. PTNS could cause pain, bruising, tingling or bleeding at the insertion site, leg cramps, numbness/pain under the sole of the foot, generalized swelling, worsening of incontinence, generalized headache and vasovagal response to needle placement, but these are rare or occasional. No serious adverse effects, like permanent or irreversible nerve damage or permanent or long-term loss of muscle function, have been reported for PTNS. TENS could cause temporary skin irritation, leg cramping or numbness/pain, however no adverse events, such as permanent or long term nerve damage or loss of muscle function, have been reported. Emotional discomfort due to the reflective nature of the questionnaires or lack of symptom improvement is also possible. Both treatment randomizations in this study are well established as options for OAB with an excellent safety profile.

Participants may also have to pay for the cost of transport to clinic visits and data charges for mobile devices for phones call or ZOOM visits.

Pregnant women will not be included in the study, so there is no risk to embryos/fetuses. If there is concern for pregnancy, we will test the participant on the day of enrollment. If they are pregnant, the patient meets exclusion criteria and will be ineligible to participate.

There are no risks to those who are not subjects.

